Appendix 12: Study Details Specific to RO7247669 2100 mg Arm

Table A12-2 Administration of First and Second RO7247669 Infusions

First Infusion	Second Infusion

• No premedication is permitted prior to the first RO7247669 infusion.• Vital signs (pulse rate, respiratory rate, blood pressure, pulse oximetry, and temperature) should be measured within 60 minutes prior to the infusion and recorded on the eCRF.• RO7247669 should be infused over 60 (± 10) minutes.• After the infusion of RO7247669, the patient begins a 60-minute observation period.• If clinically indicated, vital signs should be measured every 15 (± 5) minutes during the infusion and at 30 (± 10) minutes after the infusion. Record on the eCRF in case of abnormalities.• Patients should be informed about the possibility of delayed post-infusion symptoms and instructed to contact their study physician if they develop such symptoms.	
• If the patient experienced an IRR with the first infusion, premedication with antihistamines, antipyretics, and/or analgesics may be administered for subsequent doses at the discretion of the investigator.• Vital signs should be measured within 60 minutes prior to the infusion and recorded on the eCRF.• RO7247669 should be infused over 30 (± 10) minutes if the first infusion was tolerated without an IRR, followed by a 30-minute observation period.• If the patient experienced an IRR with the previous infusion or if clinically indicated, vital signs should be measured every 15 (± 5) minutes during the infusion and at 30 (± 10) minutes after the infusion. Record on the eCRF in case of abnormalities.

eCRF = electronic Case Report Form; IRR = infusion-related reaction.

For patients who experience a Grade 2 infusion-related reaction (IRR), premedication with paracetamol 500–1000 mg orally [PO] or IV and diphenhydramine 25–50 mg PO or IV (or an alternative histamine H_{1/2} antagonist at an adequate dose) is required prior to subsequent infusions. In case of Grade 3 or 4 IRRs related to study treatment, the patient should be permanently discontinued from the study treatment.

Guidelines for medical management of IRRs for RO7247669 are provided in Section [A12–5.1.2.3](#).

No dose modification for RO7247669 is allowed. Guidelines for treatment interruption or discontinuation because of toxicities are provided in Section [A12–5.1.2.2](#).

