Appendix 12: Study Details Specific to RO7247669 2100 mg Arm

A12–4.2 CONCOMITANT THERAPY FOR RO7247669 2100 mg ARM

Concomitant therapy consists of any medication (e.g., prescription drugs, over-the-counter drugs, vaccines, herbal or homeopathic remedies, nutritional supplements) used by a patient in addition to protocol-mandated study treatment from 7 days prior to initiation of study treatment to the treatment discontinuation visit. All such medications should be reported to the investigator and recorded on the Concomitant Medications eCRF.

A12–4.2.1 Permitted Therapy for RO7247669 2100 mg Arm

Patients are permitted to use the following therapies during the study:

- Oral contraceptives with a failure rate of <1% per year
- Hormone-replacement therapy
- Prophylactic or therapeutic anticoagulation therapy (such as warfarin at a stable dose or low-molecular-weight heparin)
- Vaccinations (such as influenza, COVID-19)

Live, attenuated vaccines are not permitted (see Section [A12–4.2.3](#))

- Megestrol acetate administered as an appetite stimulant
- Mineralocorticoids (e.g., fludrocortisone)
- Corticosteroids administered for chronic obstructive pulmonary disease or asthma
- Low-dose corticosteroids administered for orthostatic hypotension or adrenocortical insufficiency. Other use of corticosteroids may be at the investigator's discretion. The Medical Monitor is available to advise as needed.
- Local therapy (e.g., surgery other than complete lymph node dissection [CLND] that is not considered to be related to melanoma)

Premedication with antihistamines, antipyretics, and/or analgesics may be administered for the second RO7247669 infusion only, at the discretion of the investigator.

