Appendix 14: Study Details Specific to RO7247669 2100 mg + Tira Arm (Cohorts 1 and 2)

Treatment with RO7247669 may be continued during palliative radiotherapy with one exception: palliative radiotherapy is not permitted on days when RO7247669 is administered.

- Local therapy (e.g., surgery, stereotactic radiosurgery, radiotherapy, radiofrequency ablation) as outlined below:

Patients experiencing a mixed response requiring local therapy for control of three or fewer lesions may still be eligible to continue study treatment. Patients who receive local therapy directed at a target lesion will no longer be evaluable for radiographic response but will remain evaluable for progression.

Premedication with antihistamines, antipyretics, and/or analgesics may be administered for the second and subsequent RO7247669 and tiragolumab infusions only, at the discretion of the investigator.

In general, investigators should manage a patient's care (including preexisting conditions) with supportive therapies other than those defined as cautionary or prohibited therapies as clinically indicated, per local standard practice. Patients who experience infusion-associated symptoms may be treated symptomatically with acetaminophen, ibuprofen, diphenhydramine, and/or H₂-receptor antagonists (e.g., famotidine, cimetidine), or equivalent medications per local standard practice. Serious infusion-associated events manifested by dyspnea, hypotension, wheezing, bronchospasm, tachycardia, reduced oxygen saturation, or respiratory distress should be managed with supportive therapies as clinically indicated (e.g., supplemental oxygen and β2-adrenergic agonists; refer to [Appendix 8](#) for details).

A14–4.2.3 Cautionary Therapy for RO7247669 2100 mg + Tira Arm

A14–4.2.3.1 Corticosteroids, Immunosuppressive Medications, and Tumor Necrosis Factor-α Inhibitors

Systemic corticosteroids, immunosuppressive medications, and tumor necrosis factor-α (TNF-α) inhibitors may attenuate potential beneficial immunologic effects of treatment with RO7247669 and/or tiragolumab. Therefore, in situations in which systemic corticosteroids, immunosuppressive medications, or TNF-α inhibitors would be routinely administered, alternatives, including antihistamines, should be considered. If the alternatives are not feasible, systemic corticosteroids, immunosuppressive medications, and TNF-α inhibitors may be administered at the discretion of the investigator.

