Appendix 16: Study Details Specific to RO7247669 600 mg +Tira Arm

Table A16-2 Administration of First, Second, and Subsequent RO7247669 Infusions

First and Second Infusion	Subsequent Infusions

• No premedication is permitted prior to the first RO7247669 infusion.• Vital signs (respiratory rate, pulse rate, blood pressure, pulse oximetry, and temperature) should be measured within 60 minutes prior to the infusion and recorded on the eCRF.• For the first infusion, RO7247669 should be infused over 60 (± 10) minutes.• After the infusion of RO7247669, the patient begins a 60-minute observation period.• For the second infusion, RO7247669 should be infused over 30 (± 10) minutes if the first infusion was tolerated without an IRR.• If clinically indicated, vital signs should be measured every 15 (± 5) minutes during the infusion and at 30 (± 10) minutes after the infusion. Record on the eCRF in case of abnormalities.• Patients should be informed about the possibility of delayed post-infusion symptoms and instructed to contact their study physician if they develop such symptoms.	
• If the patient experienced an IRR with any previous infusion, premedication with antihistamines, antipyretics, and/or analgesics may be administered for subsequent doses at the discretion of the investigator.• Vital should be measured within 60 minutes prior to the infusion and recorded on the eCRF.• RO7247669 should be infused over 30 (± 10) minutes if the previous infusion was tolerated without an IRR.• If the patient tolerated the previous infusion of RO7247669 well without infusion-associated adverse events, the observation period may be reduced to 30 minutes.• If the patient experienced an IRR with the previous infusion or if clinically indicated, vital signs should be measured every 15 (± 5) minutes during the infusion and at 30 (± 10) minutes after the infusion. Record on the eCRF in case of abnormalities.

eCRF=electronic Case Report Form; IRR=infusion-related reaction.

For patients who experience a Grade ≥ 2 infusion-related reaction (IRR), premedication with paracetamol 500–1000 mg orally [PO] or IV and diphenhydramine 25–50 mg PO or IV (or an alternative histamine H₁/₂ antagonist at an adequate dose) is required prior to subsequent infusions. In case of Grade 3 or 4 IRRs related to study treatment, the patient should be permanently discontinued from the study treatment.

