Appendix 16: Study Details Specific to RO7247669 600 mg+Tira Arm

Table A16-4 Guidelines for Management of Patients Who Experience Adverse Events in the RO7247669 600 mg+Tira Arm (cont.)

Event	Action to Be Taken
IRRs, anaphylaxis, and hypersensitivity reactions (cont.)	
IRR to RO7247669 and/or tiragolumab Grade 1	
 Reduce infusion rate to half the rate being given at the time of event onset. After the event has resolved, the investigator should wait for 30 minutes while delivering the infusion at the reduced rate. If the infusion is tolerated at the reduced rate for 30 minutes after symptoms have resolved, the infusion rate may be increased to the original rate.
IRR to RO7247669 and/or tiragolumab Grade 2	
 Interrupt infusion. Administer aggressive symptomatic treatment (e.g., oral or IV antihistamine, anti-pyretic medication, glucocorticoids, epinephrine, bronchodilators, oxygen, IV fluids). After symptoms have resolved to baseline, resume infusion at half the rate being given at the time of event onset. For subsequent infusions, consider administration of oral premedication with antihistamines, antipyretic medications, and/or analgesics and monitor closely for IRRs.
IRR to RO7247669 and/or tiragolumab, Grade 3 or 4	
 Stop infusion. Administer aggressive symptomatic treatment (e.g., oral or IV antihistamine, anti-pyretic medication, glucocorticoids, epinephrine, bronchodilators, oxygen, IV fluids). Permanently discontinue RO7247669 and tiragolumab and contact the Medical Monitor.
Pulmonary, hepatic, GI, endocrine, ocular, immune-mediated myocarditis, CRS, pancreatic, dermatologic, neurologic, immune-mediated meningoencephalitis, renal, myositis, HLH, MAS, and systemic immune activation	
 Guidelines for the management of these events are provided in Appendix 9.

CRS=cytokine-release syndrome; GI=gastrointestinal; HLH=hemophagocytic lymphohistiocytosis; IRR=infusion-related reaction; MAS=macrophage activation syndrome.

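### In Appendices 14 and 16, premedication after a Grade 2 infusion reaction to RO7247669 is mandatory in the dosing text but only to be considered in the management table that sites are sent to

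*Combined protocol and SAP*

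**What the plan says.** **Dosing text.** Below Table A16-2 (Section A16-4.1.2.1), a patient with a Grade 2 or higher IRR is to receive paracetamol 500–1000 mg and diphenhydramine 25–50 mg, each by mouth or IV, with a substitute antihistamine allowed. The sentence ends "antagonist at an adequate dose) is required prior to subsequent infusions". The same sentence stands below Table A14-2 (Section A14-4.1.2.1). The next sentence in each place discontinues patients permanently after a treatment-related Grade 3 or 4 reaction.

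**Management table.** Table A16-4 has a row headed "IRR to RO7247669 and/or tiragolumab Grade 2". Its instruction for later doses is: "For subsequent infusions, consider administration of oral premedication with antihistamines, antipyretic medications, and/or analgesics and monitor closely for IRRs". Table A14-4 has the same heading and instruction.

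**Infusion table.** In the Subsequent Infusions column of Table A16-2, after an IRR with any previous infusion and with no grade stated, "premedication with antihistamines, antipyretics, and/or analgesics may be administered for subsequent doses at the discretion of the investigator". The same column carries the monitoring rule that begins "If the patient experienced an IRR with the previous infusion or if clinically indicated, vital signs should be measured every 15". Table A14-2 has the same layout. In both tables the other column is headed First and Second Infusion.

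**Number of infusions.** Section A16-4.1.2 gives two cycles. Section A14-4.1.2 gives two cycles in Cohort 1 and, in Cohort 2, treatment until unacceptable toxicity or loss of clinical benefit.

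**The concern.** The same appendix gives two different instructions for the same drug and the same reaction grade. They differ in force (mandatory against optional). They also differ in content: a named antipyretic together with an antihistamine, by either route, against an open choice of oral agents.

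The weaker instruction is in the place where a site would look. Sections A14-5.1.1.1 and A16-5.1.1.1, on infusion reactions to RO7247669, refer the reader to A14-5.1.4.3 and A16-5.1.4.3, which hold Tables A14-4 and A16-4. A site that follows that pointer can re-dose after a Grade 2 reaction without premedication. It would then deviate from the dosing text while complying with the management table. Both appendices list IRRs among the potential overlapping toxicities of the combination and among its adverse events of special interest.

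**Working it through.** No arithmetic underlies the conflict, so the check sets the instructions side by side.

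| Place | Trigger | Instruction for later doses |
|---|---|---|
| Text below Tables A14-2 and A16-2 | Grade 2 or higher IRR | Paracetamol plus antihistamine, oral or IV: mandatory |
| Tables A14-4 and A16-4, Grade 2 row | Grade 2 IRR to RO7247669, tiragolumab or both | Oral antihistamine, antipyretic and/or analgesic: consider |
| Tables A14-2 and A16-2, Subsequent Infusions column | IRR of any grade | Premedication at investigator discretion |

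1. **Do the first two rows overlap?** Yes. The mandatory sentence covers Grade 2 and above, but Grade 3 and 4 lead to permanent discontinuation, so a later infusion arises only after Grade 2. The management row is for Grade 2 and names RO7247669, so it cannot be read as applying to tiragolumab alone.

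2. **Does anything rank them?** No statement of precedence appears in the text examined, which runs from the end of Appendix 11 through Appendix 17. The main body, Appendices 8 and 9 and the pharmacy manuals were not available.

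3. **Is the weaker wording a deliberate choice?** No reason is given for it. In the RO7247669 monotherapy appendices, the Grade 2 lines of Tables A12-3 and A15-3 say that later doses should be given with paracetamol and an antihistamine. The optional sentence in Tables A14-4 and A16-4 matches the Grade 2 row of Table A13-5, which was written for atezolizumab and tiragolumab. A carry-over from that table is a plausible explanation, but it is an inference.

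4. **Can a Grade 2 reaction be assigned to one agent?** Usually not with confidence. Both drugs are given on Day 1 of each cycle, and Sections A14-5.1.4.2 and A16-5.1.4.2 say that events should generally be attributed to both.

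5. **Which infusions does the Subsequent Infusions column govern?** With two cycles there are 2 − 1 = 1 re-exposures, and that one is the second infusion, which belongs to the other column. Read literally, the column governs no infusion in Appendix 16 or in Appendix 14 Cohort 1, and begins at the third infusion in Cohort 2. Its IRR premedication bullet and IRR-triggered vital-signs bullet therefore miss the second infusion. The First and Second Infusion column still provides pre-infusion vital signs, a 60-minute observation period, and in-infusion vital signs if clinically indicated.

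6. **Cross-references.** The RO7247669 IRR links in A14-4.1.2.1 and A16-4.1.2.1 go to A14-5.1.2.1 and A16-5.1.2.1, the tiragolumab IRR sections. The interruption link in A16-4.1.2.1 goes to A16-5.1.2.2, which concerns immune-mediated hepatitis. The tiragolumab IRR sections themselves refer on to Tables A14-4 and A16-4, so correcting the IRR links does not resolve the conflict.

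**The case against.** The best answer is that a careful site is safe already: following the mandatory sentence satisfies every other instruction. Infusions are given in a monitored setting, the Grade 2 row asks for close monitoring, and Grade 3 or 4 reactions stop treatment. The risk text also rates cytokine-mediated IRRs on first single-agent RO7247669 dosing as low. All of this stands and limits the consequence. It does not reconcile a mandatory rule with an optional one, and sites should not have to work out which is stricter.

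A reader might infer three stronger points that the documents do not support:

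- **The infusion-table bullet is a third conflicting level.** It addresses an IRR of any grade, and the Grade 2 or higher sentence sits directly beneath it. The ordinary reading is a general permission followed by a specific rule. In Appendix 16 and Appendix 14 Cohort 1 it also governs no infusion if read literally.
- **The permitted-therapy sentences conflict too.** Section A14-4.2.2, under a Cohort 2 heading, says premedication "may be administered for the second and subsequent RO7247669 and tiragolumab infusions only, at the discretion of the investigator". Section A12-4.2.1 says "may be administered for the second RO7247669 infusion only, at the discretion of the investigator", and A15-4.2.1 says the same. None is conditional on an IRR. They grant a permission from the second infusion on. Restricting them to Grade 1 reactions would withdraw it, and tallying them as weaker instructions would mix different kinds of statement.
- **Appendices 12 and 15 share the problem.** Table A12-2 does say premedication "may be administered for subsequent doses at the discretion of the investigator", but that is again a general bullet above a specific mandatory sentence, and the management tables of those appendices broadly agree with their dosing text.

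**Conclusion.** The inconsistency is real in Appendices 14 and 16 and should be corrected at the next amendment. Its core is two table rows, the Grade 2 rows of Tables A14-4 and A16-4, against the mandatory sentence in the same appendix. A secondary layout fault leaves the IRR-specific bullets of Tables A14-2 and A16-2 off the second infusion.

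The exposure is at most one planned re-dose per patient in Appendix 16 and Appendix 14 Cohort 1, and uncapped in Cohort 2. The text gives no RO7247669 IRR rate, so the number of patients affected cannot be estimated. This is an operational safety matter, with no effect on sample size, error rates or any analysis.

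The conclusion assumes that the mandatory sentence states the intended policy, which Tables A12-3 and A15-3 support. It also assumes that no order of precedence is set in the parts of the protocol or the manuals that were not available.

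**What to change.** 1. **Tables A14-4 and A16-4, Grade 2 row.** Replace the optional wording with a requirement for paracetamol plus an antihistamine, oral or IV, before later RO7247669 infusions, matching the dosing text. Make this the default without asking sites to assign the reaction to one agent. The only exception would be a reaction that clearly occurred with tiragolumab alone.
2. **Tables A14-2 and A16-2.** Make the IRR premedication bullet and the IRR-triggered vital-signs bullet apply to the second infusion. Add to the premedication bullet a pointer to the mandatory Grade 2 rule below the table. In Table A14-2, keep both bullets for Cohort 2's later infusions. Leave the ban on premedication before the first infusion and the 60-minute observation period as they are.
3. **Housekeeping.** Point the RO7247669 IRR links in A14-4.1.2.1 and A16-4.1.2.1 to A14-5.1.4.3 and A16-5.1.4.3, and the interruption link in A16-4.1.2.1 to A16-5.1.4.2.

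Leave the permitted-therapy sentences in A12-4.2.1, A14-4.2.2 and A15-4.2.1 unchanged.

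The cost is two reworded rows, two bullets repositioned in each of two tables with one pointer added per table, and three corrected links, plus a letter to sites. No procedure is added beyond what the dosing text already requires.

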Appendix 16: Study Details Specific to RO7247669 600 mg +Tira Arm

A16-4.1.2.2 Tiragolumab

Tiragolumab will be administered by IV infusion at a fixed dose of 600 mg on Day 1 of each 21-day cycle with a post-infusion observation period as described in [Table A16-3](#).

Administration of tiragolumab will be performed in a monitored setting where there is immediate access to trained personnel and adequate equipment and medicine to manage potentially serious reactions. For anaphylaxis precautions, see [Appendix 8](#).

Tiragolumab infusions will be administered per the instructions outlined in [Table A16-3](#).

Table A16-3 Administration of First and Second Tiragolumab Infusions

First Infusion	Second Infusions

• No premedication is permitted prior to the tiragolumab infusion.• Vital signs (pulse rate, respiratory rate, pulse oximetry, blood pressure, and temperature) should be measured within 60 minutes prior to the infusion and recorded on the eCRF.• Tiragolumab should be infused over 60 (± 15) minutes.• After the infusion of tiragolumab, the patient begins a 60-minute observation period.• Record vital signs on the eCRF every 15 (± 5) minutes during the infusion and at 30 (± 10) minutes after the infusion.• Patients will be informed about the possibility of delayed postinfusion symptoms and will be instructed to contact their study physician if they develop such symptoms.	
• If the patient experienced an IRR with the first infusion, premedication with antihistamines, antipyretics, and/or analgesics may be administered for subsequent doses at the discretion of the investigator.• Vital signs should be measured within 60 minutes prior to the infusion and recorded on the eCRF.• Tiragolumab should be infused over 30 (± 10) minutes if the previous infusion was tolerated without an IRR, or 60 (± 15) minutes if the patient experienced an infusion-related reaction with the previous infusion.• Patients should be observed for 30 minutes after completion of the tiragolumab infusion if the previous infusion was tolerated without an IRR, or for 60 minutes after completion of the tiragolumab infusion if the patient experienced an IRR with the previous infusion.• If clinically indicated, vital signs should be recorded on the eCRF every 15 (± 5) minutes during the infusion and at 30 (± 10) minutes after the infusion.

eCRF=electronic Case Report Form; IRR=infusion-related reaction.

Guidelines for medical management of IRRs for tiragolumab are provided in [Table A16-4](#).

Appendix 16: Study Details Specific to RO7247669 600 mg+Tira Arm

No dose modification for tiragolumab is allowed. Guidelines for treatment interruption or discontinuation because of toxicities are provided in Section [A16-5.1.4.2](#).

Tiragolumab treatment may be interrupted for reasons other than toxicity (e.g., surgical procedures). The acceptable length of treatment interruption must be based on the investigator's benefit—risk assessment and in alignment with the protocol requirements for the duration of treatment and documented by the investigator. The Medical Monitor is available to advise as needed.

A16-4.2 CONCOMITANT THERAPY FOR RO7247669 600 mg+TIRA ARM

Concomitant therapy consists of any medication (e.g., prescription drugs, over-the-counter drugs, vaccines, herbal or homeopathic remedies, nutritional supplements) used by a patient in addition to protocol-mandated study treatment from 7 days prior to initiation of study treatment to the treatment discontinuation visit. All such medications should be reported to the investigator and recorded on the Concomitant Medications eCRF.

A16-4.2.1 Permitted Therapy for RO7247669 600 mg+Tira Arm

Patients are permitted to use the following therapies during the study:

- Oral contraceptives with a failure rate of <1% per year
- Hormone-replacement therapy
- Prophylactic or therapeutic anticoagulation therapy (such as warfarin at a stable dose or low-molecular-weight heparin)
- Vaccinations (such as influenza, COVID-19)

Live, attenuated vaccines are not permitted (see Section [A16-4.2.3](#))

- Megestrol acetate administered as an appetite stimulant
- Mineralocorticoids (e.g., fludrocortisone)
- Corticosteroids administered for chronic obstructive pulmonary disease (COPD) or asthma
- Low-dose corticosteroids administered for orthostatic hypotension or adrenocortical insufficiency. Other use of corticosteroids may be permitted at the investigator's discretion. The Medical Monitor is available to advise as needed
- Local therapy (e.g., surgery other than complete lymph node dissection [CLND] that is not considered to be related to melanoma)

A16-4.2.2 Cautionary Therapy for RO7247669 600 mg+Tira Arm

A16-4.2.2.1 Corticosteroids, Immunosuppressive Medications, and Tumor Necrosis Factor- α Inhibitors

Systemic corticosteroids, immunosuppressive medications, and tumor necrosis factor- α (TNF- α) inhibitors may attenuate potential beneficial immunologic effects of treatment

